- a. **Setting:** The study site is the medical intensive care unit (MICU) at Yale-New Haven Hospital (YNHH), York Street Campus and St. Raphael's Campus. Median ICU stay is 3 days. Predominant reasons for admission are sepsis and acute respiratory failure. MICU rooms are private. There is currently a unit-wide sleep promotion protocol which limits care activities from 00:00 to 04:00.
- b. **Design:** Aim 1 and 2, prospective cohort study; Aim 3 pilot randomized controlled trial (RCT). Aim 3 which is not dependent on Aims 1 and 2 will be conducted first.
- c. **Cohort:** We will enroll 100 subjects at risk for ICU delirium. In addition, we will enroll 16 subjects into the pilot randomize control trial.
- d. **Inclusion and exclusion criteria:** This study will focus on adults at an increased risk for ICU delirium. We have selected age ≥ 50 years as an inclusion criteria to study middle-aged to older adults who are at increasing risk for delirium while not overly restricting our sample. We will not restrict patients based on admission severity of illness (APACHE II) because we think this is a critically important confounder and would like to study the effect of the full spectrum of severity of illness on our outcomes. We will exclude patients at significant risk for pre-existing circadian abnormalities (e.g. shift work). We will also exclude patients with co-morbid disease or medication use that makes measurement of urinary aMT6s or actigraphy unreliable. Table 2 lists inclusion and exclusion criteria.

Table 2: Inclusion Criteria	Exclusion Criteria

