Research Design: For Aim 3, we will screen and enroll 16 patients using the same inclusion/exclusion criteria as Aims 1 and 2. We will collect room light levels, circadian measurements, patient characteristics, and ICU care events as before. Patients will be randomized via simple randomization with assignment via random number generator to either usual care (n=5 patients) or to bright light for 4 hours daily (n=5 patients) or to bright light for 8 hours daily (n=5 patients). The bright light intervention will be delivered from 09:00 to 13:00 daily (4 hour group) or 09:00 to 17:00 daily (8 hour group). The bright light will be delivered from study day 2 until study day 5. The bright light will continue if the patient is transferred to the floor. Bright light will be delivered by a free-standing apparatus that delivers 10,000 lux at a temperature 5000K. The device will be placed at the bedside within 36 inches of the patient's head and is expected to provide at least 1,250 lux at the angle of gaze.

To remain in the study, the patient must be in the ICU through D2 (e.g., the first day of potential intervention and the night following). After D2, bright light and other study activities will continue if the patient is transferred out of the ICU to the general medical floor. To maintain as much control of the environment as possible, study patients will be booked only to private rooms on the general medical floor.

If symptoms of eye strain, visual disturbance or headache occur, patients will not continue bright light exposure. These reversible symptoms of direct bright light therapy are unlikely, but they will be tracked as a metric of feasibility under the category of patient tolerance. Feasibility Metrics will include patient acceptance (percent of patients/surrogates who agree to bright light when described to them); patient tolerance (percent of days that patients continue with additional treatments once exposed to bright light); intervention fidelity (percent of time per day that device delivers the planned dose of light); and intervention sustainability (percent of intended intervention days that device is used).

Expected Outcomes: We expect that bright light exposure is feasible, will decrease circadian misalignment, and will increase circadian amplitude.

STATISTICAL CONSIDERATIONS

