Potential patients and/or their legally authorized representatives will be contacted in person or via the phone. Such contact will be conducted by [name] or her trained research staff.

Prior to approaching patients for study recruitment, we will obtain permission from their attending physician. Physicians in the Medical ICU will either sign a MD permission form which will provide permission to approach any of their patients or, if the physician prefers, we will request permission on a case-by-case basis.

DETERMINATION OF ELIGIBILITY

Eligibility will be determined by study staff via review of the electronic medical record; staff will be appropriately trained in HIPAA, screening and consent and enrollment procedures. Currently this will be PI [name] and other staff will be added to the protocol when identified and trained.

ASSESSMENT OF CURRENT HEALTH PROVIDER RELATIONSHIP FOR HIPAA CONSIDERATION

It is possible that some of the research subjects may be on the MICU service for which [name], [name] or [name] are the attending. This will be a relatively rare event. Participation in the study will not alter usual MICU care (other than possible Daytime Bright Light for Aim 3 subjects randomized to this intervention).

REQUEST FOR WAIVER OF HIPPA AUTHORIZATION FOR RECRUITMENT/ SCREENING

This study was granted a waiver of HIPPA Authorization for recruitment and screening procedures.

PROCESS OF CONSENT/ASSENT

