Skin irritation from the Actiwatch Spectrum or iButton device can be mitigated by movement of device to a contralateral site. If skin irritation is severe, the Actiwatch Spectrum or iButton will be removed, and study participation will be discontinued. If symptoms (eye strain, visual disturbance or headache) develop, light therapy will be discontinued, and the side effect will be tracked as a metric of feasibility. In addition, hypomania and mania in patients with a history of bipolar disease have also been reported as uncommon but serious side effects of overexposure to light therapy. Patients with a history of bipolar disease will be excluded from the study.

DATA AND SAFETY MONITORING PLAN

[figure not shown]
Data and Safety Monitoring for Clinical Trials: This protocol presents minimal risks to the subjects and Unanticipated Problems Involving Risks to Subjects or Others (UPIRSOs), including adverse events, are not anticipated. In the unlikely event that such events occur, the following Data and Safety Monitoring for Clinical Trials Plan will be followed.

Main Study DSMP

A **medical monitor** will oversee the proposed research project. **[name]**, Yale-New Haven Hospital MICU attending and board certified in critical care medicine, has agreed to serve as project medical monitor. She has no conflicts of interest with this role. [name] will conduct interim monitoring of accumulated data from research activities to assure the continuing safety of participants and integrity of the accumulating data. The medical monitor is independent of the study investigative team and will report progress including safety concerns to the project principal investigator. Safety concerns will be also be reported to the IRB.

- 1. Safety:** Safety will be monitored at intervals related to patient enrollment. Safety and device protocols will be reviewed by the medical monitor every twenty patients to assure uniform and safe application of project devices. Research staff will report skin irritation or bright light related symptoms as they occur via event evaluation forms. In addition, research staff will identify and immediately report unanticipated problems, unexpected adverse events and serious adverse events (defined below). Safety concerns will be also be reported to the IRB.

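### The medical monitor's every-twenty-patients review would miss the 16-patient bright-light pilot, which is conducted first and is the only part of the project that uses the lamp

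*Combined protocol and SAP*

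**What the plan says.** The Data and Safety Monitoring Plan (Main Study DSMP, item 1, Safety) paces safety monitoring by enrollment and gives one interval: "Safety and device protocols will be reviewed by the medical monitor every twenty patients to assure uniform and safe application of project devices".

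Project Overview, item b (Design), sets the order of the work: "Aim 3 which is not dependent on Aims 1 and 2 will be conducted first". Item c (Cohort) gives the size: besides a cohort of 100, "we will enroll 16 subjects into the pilot randomize control trial". The Aim 3 Research Design repeats 16 but lists three arms of five: usual care, 4 hours of light daily, and "bright light for 8 hours daily (n=5 patients". On duration it says: "The bright light will be delivered from study day 2 until study day 5".

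The lamp belongs to the pilot alone. The section on current health provider relationships says participation leaves usual MICU care unchanged, "other than possible Daytime Bright Light for Aim 3 subjects randomized to this intervention".

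The monitor has other duties with no stated interval: interim monitoring of accumulated data, a compliance check on a random one in ten patients, and evaluation of adverse events as they are reported.

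**The concern.** The stated purpose of the twenty-patient review is that project devices be applied uniformly and safely. The lamp is the only experimental exposure in the project, and it is used only in a part that ends before patient 20. On the stated numbers, the first scheduled review could not change how the lamp is placed or run for any pilot patient.

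Event-driven reporting starts from a symptom or event that someone notices. It does not bring a misplaced lamp or an under-delivered dose to the monitor if nobody has a complaint. Some patients will be delirious or unable to communicate and enrolled through a representative, so it is reasonable to infer that not all can report eye strain or headache.

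Delivered light is also uncertain in the protocol's own figures. The Aim 3 Research Design expects at least 1,250 lux at the angle of gaze with the lamp within 36 inches. Study Risks says the light falls below 1,250 lux at 36 inches. Those two statements must be reconciled. Uneven application would also affect the feasibility result, since fidelity is one of four metrics that must reach 70% (Aim 3 Analytical Approach).

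**Working it through.** **Inputs**

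- Review interval: 20 patients, counted by enrollment (monitoring plan, item 1).
- Pilot size: 16 (Project Overview, item c; Aim 3 Research Design), or 5 + 5 + 5 = 15 from the listed arms.
- Cohort size: 100 (Project Overview, item c).
- Order: pilot first (Project Overview, item b).
- Light: days 2 to 5, taken as inclusive, so 4 days, at 4 or 8 hours a day (Aim 3 Research Design).

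**Scheduled reviews inside the pilot**, as floor(n / 20):

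- n = 16: floor(16/20) = 0
- n = 15: floor(15/20) = 0

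The result is the same whether the count runs on into the cohort or restarts with each aim.

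**Scheduled reviews over the whole project:** floor((16 + 100)/20) = 5 and floor((15 + 100)/20) = 5, at total enrollment 20, 40, 60, 80 and 100. Subtracting the pilot gives the place of each review in the cohort:

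| Pilot size | Cohort patient at each review |
|---|---|
| 16 | 4, 24, 44, 64, 84 |
| 15 | 5, 25, 45, 65, 85 |

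**Planned light exposure finished before the first review**, using the listed arms:

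- Patients: 5 + 5 = 10
- Patient-days: 10 × 4 = 40
- Hours: (5 × 4 days × 4 h) + (5 × 4 days × 8 h) = 80 + 160 = 240

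The arm of a 16th patient is not stated. That patient would add 0, 16 or 32 hours, giving a range of 240 to 272. These totals are nominal: simple randomization does not guarantee 5/5/5, and early discharge or stopping would lower them.

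**When the zero would become one:** 20 − 16 = 4 (or 20 − 15 = 5) further patients would have to enroll before the last pilot patient finishes. They could be early cohort patients, because running the pilot first does not rule out overlap. They could also be replacements: "To remain in the study, the patient must be in the ICU through D2", and the plan does not say whether patients who leave are replaced. Either way the review comes at the 20th enrollment, late in the pilot.

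**The one-in-ten compliance check** would select on average 16/10 = 1.6 (or 15/10 = 1.5) pilot patients. It is a sampling fraction, not a time point. It covers IRB requirements, consent, source documents and investigator compliance, and neither names nor excludes device use.

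**The case against.** The strongest reply is that this is a preference about monitoring intensity and not an error. The plan sets one cadence for the project and never promises a review during the pilot. The scheduled item is narrow, since it speaks of reviewing protocols, and the devices in question include the wrist actigraph and the iButton as well as the lamp.

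Safety in the pilot is also largely covered elsewhere. Light symptoms are reported as they occur, and light is discontinued if they develop. Every adverse event goes to the monitor for grading. Related serious or unexpected events reach the IRB and NHLBI within 5 days. Interim monitoring of accumulated data is promised for the whole project. Uniform delivery is itself a pilot outcome through "intervention fidelity (percent of time per day that device delivers the planned dose of light", alongside room light logged every 10 seconds. Study Risks calls the risk minimal and the light symptoms minor and reversible. Finally, the zero is conditional: with a median ICU stay of 3 days, four replaced dropouts would bring enrollment to twenty within the pilot.

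Most of this stands, and it limits the weight of the point. The pilot is not without safety oversight, and the light-hour totals describe the pilot's planned size and do not measure harm. But none of these provisions puts a monitor review of device application inside the pilot. The interim monitoring has no date, the fidelity data are collected without a stated time for the monitor to see them, and a review at the 20th enrollment would leave little of the pilot to correct.

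**Conclusion.** The point holds. As written, none of the project's five scheduled monitor reviews falls in the only part that uses the lamp, and all planned light exposure (10 patients and 40 patient-days by the listed arms) would be complete before the first.

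This assumes that the pilot finishes enrolling and treating before 4 (or 5) other patients enter, and that the one-in-ten check is read as a sampling fraction. The difference between 16 and 15 does not affect the conclusion. The arithmetic is certain, while the practical consequence is modest given the low described risk and the event-driven reporting. It should be changed because the rule cannot serve its own purpose where that purpose matters most, and the change is cheap.

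**What to change.** Add one sentence to item 1 of the monitoring plan giving Aim 3 its own trigger: at least one medical-monitor review during the pilot, for example about halfway, after the 8th randomised patient (16/2 = 8). It should cover accumulated safety events and device application, using the light-meter and fidelity data already collected, and state that this is when the promised interim monitoring takes place for Aim 3. The twenty-patient interval can stay for Aims 1 and 2. The exact patient number is the sponsor's choice.

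The cost is one sentence and one short additional review by the monitor already appointed. That review is slightly wider than the protocol review now described, so it takes a little more monitor time. No new patient measurements are needed and treatment does not change.

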- 2. Protocol Compliance:** The project medical monitor will check enrolled patients for compliance with IRB requirements, conformance with informed consent procedures, verification of source documents and investigator compliance. One in ten patients will be randomly selected for conformance.
- 3. Event Evaluation:** Adverse event or unanticipated problem occurrence will prompt an event evaluation and a report to the project medical monitor. The adverse event report will NOT include identifying patient information but will otherwise provide a clinical summary of the study patient and the circumstances immediately associated with the adverse event / unanticipated problem including date of the event, type of event and a narrative event description.

Flow Diagram for Adverse Event / Unanticipated Problem Detection, Review and Reporting:

Unanticipated Problems are defined as any incident, experience, or outcome that meets all of the following criteria: 1) unexpected, 2) related or possibly related to participation in the research, and 3) suggests that the research places subjects or others at a greater risk of harm than was previously known or recognized.

Adverse Events: An **adverse event** will be defined as any untoward or unfavorable medical occurrence in a human subject, including any abnormal sign, symptom, or disease, temporally associated with the subject's participation in the research, whether or not considered related to the subject's participation in the research (modified from the definition of adverse events in the 1996 International Conference on Harmonization E-6 Guidelines for Good Clinical Practice). Adverse events that occur during study enrollment will be reported by research staff to the project medical monitor via an event evaluation.

A serious adverse event is any adverse event temporally associated with the subject's participation in research that meets any of the following criteria (modified from the definition of serious adverse drug experience in FDA regulations at 21 CFR 312.32(a)):

1. results in death or is life-threatening
2. requires prolongation of existing hospitalization
3. results in a persistent or significant disability/incapacity
4. results in a congenital anomaly/birth defect
5. any other adverse event that, based upon appropriate medical judgment, may jeopardize the subject's health and may require medical or surgical intervention to prevent one of the other outcomes listed in this definition

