Response to Adverse Event: All study patients are (by definition) concurrently admitted to the MICU. The response to any adverse event will be appropriate medical care. Adverse event occurrence will prompt an event evaluation and report to the project medical monitor by research staff.

The project medical monitor will evaluate adverse events along the parameters of relationship, severity, and expectedness:

Relatedness:

1. Unrelated: Adverse event(s) clearly not related to the project
2. Unlikely: Adverse event(s) doubtfully related to the project
3. Possibly: Adverse events(s) may be related to the project; known to occur, but the temporal relationship is unclear; other causes are possible or biologically very plausible
4. Probably: Adverse event(s) likely associated with the project; known to occur and temporal relationship is appropriate; other causes are unlikely
5. Definitely: Adverse event(s) clearly associated with the project

Severity: The following scale will be used to grade the severity of adverse events noted during the study:

1. Mild adverse event: Did not interfere with normal activity, minimal symptoms, no intervention required
2. Moderate adverse event: Interfered with normal activity to some extent, moderate symptoms, minimal or local intervention required
3. Severe adverse event: Prolonged hospitalization with need for intervention to prevent escalation of condition
4. Life-threatening / disabling adverse event: Event that puts the patient at risk of death at the time of the event if immediate intervention is not undertaken
5. Fatal adverse event

Expectedness: An unexpected adverse event is any adverse event occurring in one or more subjects in a research protocol, the nature, severity, or frequency of which is not consistent with either (1) the known or foreseeable risk of adverse events associated with the procedures involved in the research that are described in (a) the protocol-related documents such as the IRB-approved research protocol and the current IRB-approved informed consent document, and (b) other relevant sources of information, such as product labeling and package inserts; or (2) the expected natural progression of any underlying disease, disorder, or condition of the subject(s) experiencing the adverse event and the subject's predisposing risk factor profile for the adverse event.

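### The severity scale defines grade 3 by length of stay and grade 4 only by risk of death, so an intense or disabling event that does neither has no grade above moderate

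*Combined protocol and SAP*

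**What the plan says.** The severity scale is in the Data and Safety Monitoring Plan, under Response to Adverse Event. Its scope is general: "The following scale will be used to grade the severity of adverse events noted during the study". The grader is named: "The project medical monitor will evaluate adverse events along the parameters of relationship, severity, and expectedness". The Safety item of the same plan routes skin irritation and light-related symptoms into this process through event evaluation forms.

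The grades that matter here are:

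- Grade 2: "Moderate adverse event: Interfered with normal activity to some extent, moderate symptoms, minimal or local intervention required".
- Grade 3: "Severe adverse event: Prolonged hospitalization with need for intervention to prevent escalation of condition".
- Grade 4, titled as life-threatening or disabling: "Event that puts the patient at risk of death at the time of the event if immediate intervention is not undertaken".

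The SAE definition in the same plan includes, as item 2, an event that "requires prolongation of existing hospitalization" and, as item 3, one that "results in a persistent or significant disability/incapacity".

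The word *severe* also appears earlier, under Minimizing Risks: "If skin irritation is severe, the Actiwatch Spectrum or iButton will be removed, and study participation will be discontinued". That section neither defines the word nor points to the scale.

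**The concern.** Severity (how intense an event is) and seriousness (what outcome it led to) are separate attributes, and the plan asks for both. Grades 1 and 2 follow that separation. Grade 3 abandons it and uses an outcome that the SAE definition already captures. Grade 4 promises in its title to cover disability and then does not.

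The harms that the plan itself foresees are headache, eye strain, disturbed vision and skin irritation. Where one of these is intense but does not extend the stay or threaten life, the medical monitor has no grade whose wording fits. A summary with no severe light or device events would then partly reflect how the scale is worded. The pilot sets out to show that bright light is acceptable and tolerable, so its safety record should be able to show the opposite.

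**Working it through.** No arithmetic applies. The check sets the grade definitions beside the SAE criteria and then follows the grade to where it is used.

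**Step 1. What each grade is defined by, and whether an event that meets the text is automatically serious.**

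| Grade | Defined by | SAE item met by definition |
|---|---|---|
| 1 Mild | Intensity: interference, symptoms, intervention | None |
| 2 Moderate | Intensity: interference, symptoms, intervention | None |
| 3 Severe | Outcome: longer stay, with intervention needed | Item 2 (prolongation) |
| 4 Life-threatening / disabling | Risk of death only | Item 1 (life-threatening) |
| 5 Fatal | Death | Item 1 (death) |

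All three upper grades imply an SAE. A severe but non-serious event cannot be recorded under the text as written.

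**Step 2. Test cases.** Each is assumed neither to lengthen the stay nor to threaten life.

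| Event | Grade 2 text | Grade 3 text | Grade 4 text | SAE? |
|---|---|---|---|---|
| Intense headache or eye strain | Not met: symptoms exceed moderate | Not met: no longer stay | Not met: no risk of death | Not through items 1 to 4; item 5 is by judgment |
| Marked skin injury needing more than local treatment | Not met: exceeds minimal or local intervention | Not met | Not met | As above |
| Lasting, disabling visual deficit | Not met | Not met | Title met, definition not met | Yes, item 3 |

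The first two rows fall between grades 2 and 3. The third is serious by item 3 and fits the grade 4 title, but meets no definition above grade 2.

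**Step 3. Where the grade is used.**

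- *Recorded severity.* Used directly: the medical monitor assigns it to each reported event.
- *Expectedness.* Used indirectly. An event can be unexpected because its severity is out of line with the known risk, and Study Risks describes the light effects as minor and reversible. The plan does not say that this comparison uses the numeric grade.
- *Feasibility.* Not used. Under Aim 3, tolerance is the percent of days on which exposed patients continue treatment, and feasibility requires at least 70% on each metric.
- *Stopping light.* Not used. The plan stops light for any of the listed symptoms, whatever the grade.
- *5-day report to the IRB and the funder.* Not used directly. It depends on unanticipated, unexpected or serious status together with relatedness.

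**Step 4. The two uses of *severe*.** Under Minimizing Risks the word is undefined and stands in a rule on device removal and participation. In the scale it is tied to a longer stay and is assigned by the medical monitor on an event report. Nothing in the plan connects the two or says that they are separate.

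**The case against.** The strongest reply is that little depends on the grade. Step 3 bears this out for feasibility, for stopping light and for the direct reporting triggers, and the statistical section plans no analysis by severity grade. The event report must include a narrative, so intensity is not lost altogether. A lasting visual deficit is an SAE by item 3, and item 5 lets medical judgment capture other important injuries. A monitor could also rely on the grade 4 title for a disabling event. All of this stands and limits the reach of the point. It does not repair the scale: the definitions still leave a gap, and title and text still disagree.

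A reader might infer four stronger things that the documents do not support:

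- *That the rule on severe skin irritation can hardly ever be met.* This follows only if *severe* there means grade 3. The plan does not say so, and staff could use the ordinary meaning.
- *That the tolerability conclusion is biased by construction.* The tolerance metric counts days of continued treatment. A symptom that stops light counts against it at any grade.
- *That 5-day reporting fails because prolongation is known late.* Grade 3 does not start that clock. Late knowledge of a longer stay concerns SAE item 2, which rewording the grades would not change.
- *That intense events are capped at moderate.* That may be the practical result, but an intense event does not fit the grade 2 text either. The defect is a gap, and graders have no rule for it.

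**Conclusion.** The point holds as a defect in a stated rule and should be corrected. Grade 3 has no intensity criterion and overlaps SAE item 2. The grade 4 definition omits the disability that its title announces. An intense or disabling event that neither lengthens the stay nor threatens life therefore meets no definition above grade 2.

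The size is limited. The defect affects the grades that the medical monitor records and, indirectly, the judgment of expectedness. It changes no endpoint, feasibility judgment or direct reporting trigger. How many events would be affected cannot be stated: the plan gives no rate for the foreseen harms and none for how often they lengthen a stay. That they would rarely do so is an assumption. The conclusion about the gap does not need it; only the likely number of affected events does.

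The two uses of *severe* need to be reconciled. That is a clarification, and it is not evidence that the skin-irritation rule fails.

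**What to change.** Three wording changes:

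1. Define grade 3 by intensity, continuing the terms of grades 1 and 2 (degree of symptoms, interference and intervention), and leave prolongation of stay to the SAE criteria.
2. Make the grade 4 definition cover disability, so that it agrees with its own title and with SAE item 3.
3. Under Minimizing Risks, state whether *severe* skin irritation refers to this scale. Any clinical threshold or action is for the investigators, and none is proposed here. If the rule is to be tied to the scale, they need to consider change 1 with that in mind.

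The cost is a protocol edit. Visits, data collection and sample size do not change. The downside is that some events may be graded higher than under the current wording.
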